15.1 Sample Size

Up to approximately 183 patients will be enrolled.

15.2 Data Sets Analyzed

All patients who have received study medication will be included in the Safety population for safety analysis.

15.3 Demographic and Baseline Characteristics

The following demographic and baseline variables will be summarized:

- Demographics
- Extension Day 1 predose vital signs and laboratory tests

15.4 Patient Disposition

The number and percent of patients who complete or discontinue from the study will be summarized. The reasons for study discontinuation will be included in the summary.

15.5 Analysis of Safety Endpoints

Adverse Events: All AE will be coded using the Medical Dictionary for Regulatory Activities (MedDRA) and will be classified by MedDRA system organ class and preferred term. Listings will include all AE collected on study. The summaries of AE will be based on TEAE, defined as an AE reported in the clinical database with a date of onset (or worsening) on or after the start date of the first intravenous infusion of the study medication.

Patient incidence (N and %) of TEAE will be summarized as follows:

- Overview of TEAE to include
 - Number (%) of patients who report at least one TEAE overall, by severity and by relationship
 - Number (%) of patients who report at least one serious TEAE
 - Number (%) of patients who report at least one TEAE leading to treatment discontinuation
 - Number (%) of patients who report at least one TEAE of special interest
- TEAE by preferred term
- TEAE by system organ class and preferred term

- TEAE by maximum severity, system organ class, and preferred term
- Drug-related TEAE by system organ class and preferred term
- TEAE leading to withdrawal by system organ class and preferred term
- Serious TEAE by system organ class and preferred term
- TEAE of special interest by system organ class and preferred term

Clinical Laboratory Assessments: Samples will be obtained for the clinical laboratory tests identified in Section 11.4, and laboratory tests to be summarized include blood chemistry, hematology, urinalysis, and ADA.

Descriptive statistics will be used to summarize laboratory results at baseline, each visit, and the change from baseline for each visit. In addition, shift tables will summarize the laboratory results relative to normal reference ranges at baseline and each post-baseline time point.

Vital Signs: Vital signs will be summarized at baseline, each visit, and change from baseline at each visit.

Physical Examination: New or worsening symptoms in the symptom-directed physical examinations will be included in the by-patient data listings.

Concomitant Medications: All medications will be coded using the most current World Health Organization Drug Dictionary. Concomitant medications will be summarized by Anatomical Therapeutic Chemical Class and preferred term.

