Test Product, Dose, and Administration	
AK002 ([REDACTED]) is supplied as a sterile liquid and will be diluted with 0.9% sodium chloride (NaCl) for intravenous injection. The injection will be administered by IV infusion as specified in the Pharmacy Manual.
 
AK002 is formulated in [REDACTED] pH 6.0, in Water for Injection (WFI).
 
There is no placebo in this study.
 
AK002 at a dose of 3 mg/kg will be prepared according to the patient's body weight. Dosing will occur every 28 (± 3) days for a total of 18 monthly doses. Dosing will occur on Days 1, 29, 57, 85, 113, 141, 169, 197, 225, 253, 281, 309, 337, 365, 393, 421, 449, and 477 (± 3 days).
 
Twelve to 24 hours prior to the first infusion of AK002, 80 mg oral prednisone will be self-administered by the patient. A steroid premedication prior to the start of any subsequent infusions may only be administered with the written approval of the Medical Monitor.
 
The initial infusion should be given over at least a 4-hour period. The second and subsequent infusions can be given over at least a 2-hour period, depending on the patient's tolerance of the previous infusions and at the Investigator's discretion. After the sixth infusion, a 1-hour infusion rate may be utilized.
 
Any changes in the infusion rate schedule due to tolerability will not be considered deviations from the protocol, as long as the maximum infusion speed is not exceeded/increased beyond the protocol specified limits.
 
All infusions must be completed within 8 hours of AK002 being mixed with NaCl.

Duration of Patient Participation	
The total study duration for each patient will be approximately 21 months. This includes:
 
• Treatment period of approximately 18 months• Post-treatment follow-up period of 84 days (± 3 days) following last dose of AK002.

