7.4 Exclusion Criteria

Patients will be excluded from the study if they meet any of the following criteria:

- 1) Poor tolerance to previous administration of AK002 in the opinion of the Investigator.
- 2) Known hypersensitivity to any constituent of the study drug.
- 3) Any disease, condition (medical or surgical), or cardiac abnormality, which, in the opinion of the Investigator, would place the patient at increased risk.
- 4) Planned or expected vaccination with live attenuated vaccines during the treatment period, or vaccination expected within 5 half-lives (4 months) of AK002 administration. All types and formulations of vaccines (including live attenuated vaccines) authorized by FDA or other regulatory authority for the prevention of COVID-19 may be administered before, during, or after this study. The vaccine should not be administered within 7 days prior to and within 7 days after the administration of AK002 so that any side effects caused by either of the 2 medications can be more easily determined.
- 5) Women who are pregnant, breastfeeding, or planning to become pregnant while participating in the study.
- 6) Any other reason that, in the opinion of the Investigator or Medical Monitor, makes the patient unsuitable for enrollment.

8. Concurrent Medications

Prior and concomitant medications include both prescribed and over-the-counter medications and will be recorded in the electronic Case Report Forms (eCRF). Medications taken for EG/EoD or symptoms of EG/EoD, as well as any medications taken within 30 days prior to extension study Day 1 should be recorded.

Medications taken prior to the study should be maintained, as much as possible. Patients should be advised against taking any new medication or stopping an existing medication, both prescribed and over-the-counter, without consulting the Investigator, unless the change is required for emergency use. Immediately prior to the first infusion, the study site personnel should ensure that the patient continues to meet the inclusion criteria and none of the exclusion criteria (including use of prohibited medications as per AK002-016 criteria).

All medications used during the conduct of the study must be documented.

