13.1 Adverse Events

In accordance with 21 Code of Federal Regulation (CFR) 312.32(b) and International Conference on Harmonisation (ICH) Guidance E2A, an adverse event is any untoward medical occurrence in a clinical investigation of a patient administered a pharmaceutical product and that does not necessarily have a causal relationship with the treatment. An AE is therefore any unfavorable and unintended sign (including an abnormal laboratory finding), symptom, or disease temporally associated with the administration of an investigational product, whether or not related to that investigational product. An unexpected AE is one of a type not identified in nature, severity, or frequency in the current Investigator's Brochure or of greater severity or frequency than expected based on the information in the Investigator's Brochure.

Examples of an AE include:

- Significant worsening or exacerbation of underlying medical condition.
- Significant abnormal findings from physical examinations, vital signs or laboratory tests.

The following examples are not considered AE:

- Medical or surgical procedure, although the condition leading to the procedure is usually an AE.
- Anticipated day-to-day fluctuations of preexisting medical conditions (including laboratory values) as long as worsening from baseline does not occur.
- Signs or symptoms of the disorder being studied unless they become more severe or occur with a greater frequency than occurring at baseline.
- Normal progression of the disorder being studied unless it is more severe or occurs with greater speed/frequency than expected.

All AE, whether elicited by questions from study staff, volunteered, or noted on physical examination/laboratory testing, and regardless of causality or severity, will be assessed and recorded in the eCRF beginning after the first administration of study drug and ending on Extension Day 561 or 84 (± 3) days after last dose of study drug if ET.

The assessment of an AE will be done pursuant to definitions set forth by ICH Good Clinical Practice (GCP) guidelines and applicable regulatory requirements.

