13.7 Adverse Event Reporting Procedures

13.7.1 All Adverse Events

Any clinically significant AE that is ongoing at the time of study completion or ET will be followed by the Investigator until event resolution, the AE is otherwise explained, the AE is not considered clinically significant by the Investigator, or the patient is lost to follow-up.

All non-serious AE identified will be recorded in the Adverse Event eCRF beginning from the time of first study drug infusion and ending on Extension Day 561 (± 3) or 84 (± 3) days after last dose of study drug if ET. All SAE identified will be recorded in the Adverse Event eCRF beginning from the time of first study drug infusion and ending on Extension Day 561 (± 3) or 84 (± 3) days after last dose of study drug if ET. Whenever appropriate, the CTCAE (version 5.0 or most current version) should be used for naming common AE ([Appendix 3](#)).

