14.2 Early Discontinuation of Study Drug

A patient may be discontinued from study treatment at any time if the patient, the Investigator, or the Sponsor feels that it is not in the patient's best interest to continue. The following is a list of possible reasons for study treatment discontinuation:

- Patient withdraws consent.
- An AE that in the opinion of the Investigator results in it being in the best interest of the patient to discontinue study treatment.
- Protocol violation requiring discontinuation of study treatment.
- Participation in any other study during the duration of this study.
- Use of a non-permitted concomitant drug without prior approval from the Medical Monitor.
- Loss of ability to freely provide consent through imprisonment or involuntary incarceration for treatment of either a psychiatric or physical (e.g., infectious disease) illness.

If a patient is withdrawn from treatment due to an AE, the patient will be followed and treated by the Investigator or designee until the abnormal parameter or symptom has resolved or stabilized.

All patients who discontinue study drug treatment should be encouraged to continue on study and complete assessments and procedures according to [Table 1](#), if possible.

Reasonable attempts will be made by the Investigator to provide reasons for patient withdrawals. The reason for the patient's withdrawal from the study or all attempts to acquire such, will be specified in the source documents.

15. Statistical Methods and General Considerations

This section outlines the nature and rationale for the statistical methods to be used for analysis of the data from the study. A separate Statistical Analysis Plan will describe data handling and statistical techniques in full detail. The Statistical Analysis Plan will contain any modifications to the analysis plan described below.

All patient data will be listed. When appropriate, summary statistics of number of non-missing values, mean, median, standard deviation, minimum, and maximum will be computed for continuous variables, and summary statistics of number and percentage will be computed for categorical variables. No formal statistical inferences will be made. No imputation will be used for missing data.

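### The TEAE definition has no end date, so a patient who stops AK002 early but stays on study has 112 to 560 off-drug days counted as treatment-emergent, against 84 (±3) for one who leaves or completes dosing

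*Combined protocol and SAP*

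**What the plan says.** Section 15.5 bases the AE tables on TEAEs, which are database events "with a date of onset (or worsening) on or after the start date of the first intravenous infusion of the study medication". No lag after the last dose is given. The results are numbers and percentages of patients: overall, serious, leading to discontinuation, of special interest, and by term.

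Section 13.1 starts AE capture at the first dose and sets its end as "ending on Extension Day 561 or 84 (± 3) days after last dose of study drug if ET". Here ET means early termination. Section 13.7.1 repeats this window for non-serious and serious events, and Section 13.3 does so for AESIs. Section 5.1 links ET to the study rather than to the drug alone, and Table 1 note 23 ties the early-termination biopsy to discontinuing the study.

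The sentence in Section 14.2 on patients who stop drug reads, up to its reference to Table 1: "All patients who discontinue study drug treatment should be encouraged to continue on study and complete assessments and procedures according to". It adds that this applies only where feasible. Section 14.1 defines completion by visits through Day 561 and sets no condition on doses received. The Synopsis gives the planned off-drug period as "Post-treatment follow-up period of 84 days (± 3 days) following last dose of AK002".

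**The concern.** Under these rules, two patients with identical exposure can have very different TEAE windows. The difference depends only on whether each remains in the study after stopping drug. For the patient who stays, an event a year or more after the last infusion is tabulated together with events on treatment.

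Long-term safety is a stated objective, and every AE table in Section 15.5 rests on this definition. No listed table gives the incidence on treatment plus the protocol's own 84-day follow-up, and none splits on-treatment from post-treatment events. Late off-drug time may also include events under other medication: use of a non-permitted drug is a listed reason for stopping AK002 (14.2), the prohibited list includes immunosuppressants (8.1), and opportunistic infection is an AESI (13.3). Such an infection many months after the last AK002 dose would count as a TEAE of special interest.

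This question is separate from adjusting incidence for length of follow-up. An exposure-adjusted rate changes the denominator but not which events are called treatment-emergent.

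**Working it through.** **Inputs from the protocol.** There are 18 doses every 28 days from Day 1 to Day 477 (9.4). AE capture ends on Day 561, or 84 (±3) days after last dose if ET (13.1). Enrolment is up to about 183 (15.1).

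**The plan's own figure.** Dose k falls on Day 1 + 28(k − 1). Dose 18 is on Day 477, and 477 + 84 = 561. For a patient who takes every dose the two end dates coincide.

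**Off-drug days counted as treatment-emergent for a patient who stays.** The formula is 561 − [1 + 28(k − 1)] = 560 − 28(k − 1).

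| Last dose | Day | Stays to Day 561 | Leaves (ET) | Excess |
|---|---|---|---|---|
| 1 | 1 | 560 | 84 | 476 |
| 3 | 57 | 504 | 84 | 420 |
| 6 | 141 | 420 | 84 | 336 |
| 11 | 281 | 280 | 84 | 196 |
| 17 | 449 | 112 | 84 | 28 |
| 18 | 477 | 84 | – | 0 |

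The 84 for a leaver is nominal: ±3 days, fewer if consent is withdrawn, and more if the patient is off drug for over 84 days before leaving.

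**Late off-drug time.** Assume that k is uniform on 1 to 17. Mean off-drug time is then (112 + 560)/2 = 336 days, or 336 − 84 = 252 days beyond the window. If 10–30% of 183 patients stop and stay to Day 561 (assumption):

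- 183 × 0.10 × 252/365.25 = 12.6 patient-years
- 183 × 0.30 × 252/365.25 = 37.9 patient-years

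The maximum possible time is 183 × 560/365.25 = 280.6 patient-years, so these are 4.5% and 13.5% of it.

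**Effect on the overall TEAE percentage.** Patients with a TEAE inside the window already count, so only a first event after it adds to the percentage. Assume a constant rate r per patient-year, on and off drug. For a stopper at dose k, the chance of a first event after the window is

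exp[−r(28(k − 1) + 84)/365.25] − exp[−r × 560/365.25].

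Averaged over k = 1 to 17:

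- r = 0.5: 0.668 − 0.465 = 0.203. Multiplied by 10% and 30%, this is 2.0 and 6.1 points.
- r = 1: 0.461 − 0.216 = 0.245. Multiplied by 10% and 30%, this is 2.5 and 7.4 points.

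The range is about 2 to 7 percentage points. Individual terms will differ.

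**The case against.** **The schedule may intend 84 days for everyone.** The Synopsis and 5.1 say without condition that patients are followed for 84 days after last dose, and the headings of 12.13 to 12.15 omit the ET qualifier. Apart from the Day 211 EGD, the treatment-period columns of Table 1 are dosing visits. Section 14.2 only encourages staying. This leaves room for doubt about intent, but the capture rule in 13.1, the use of ET in 5.1 and note 23, and completion by visits in 14.1 all point to Day 561 for a patient who stays. If 84 days was meant for all, 15.5 should say so.

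**Treatment-emergent is not the same as attributed to treatment.** A reader might infer that late events are blamed on AK002. The documents do not support that. Section 13.6.3 grades causality and lets remote timing count against a relationship, and 15.5 reports by relationship and has a drug-related table. That mitigates the drug-related summaries only. The overall, serious and AESI percentages are not restricted by causality.

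**Relapse.** A reader might also infer that any return of EG/EoD after washout becomes a TEAE. Section 13.1 excludes symptoms of the disease under study unless they are more severe or more frequent than at baseline, so a return to the baseline level is not an AE.

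**An inclusive window is conservative, and 84 days is short.** This has force. Section 7.4 equates five half-lives with four months ("vaccination expected within 5 half-lives (4 months) of AK002 administration"), and 7.3 uses 120 days after last dose for contraception. A cut at 84 days alone would move events at 85–120 days, including infection AESIs, out of the headline table. The remedy therefore has to show that interval and keep the end-of-study counts.

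**The SAP may settle it.** Section 15 defers full detail to a separate SAP, which is not in the document reviewed. An end date could be there. Section 15.5 also lists all AEs, so a later split would need no new data.

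**Conclusion.** The point holds. Section 15.5 bounds a TEAE only at its start. As written, early stoppers who stay have 112 to 560 off-drug days counted as treatment-emergent, against 84 (±3) for leavers and for patients who take all 18 doses. The headline percentages therefore depend partly on who stays.

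It would be wrong to treat 560 days as typical: it needs a single dose followed by staying to Day 561, and it falls by 28 days with each further dose. The documents do not say how many patients stop and stay, so the real effect on the tables cannot be computed. The figure of 2 to 7 points on the overall percentage assumes that 10–30% stop and stay to Day 561, uniform stopping times, and a constant 0.5–1 AE per patient-year.

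Nor is any test or error rate at risk. The study is single-arm, and Section 15 rules out formal inference. What suffers is the interpretation of the safety percentages. The correction should be made, but it is a matter of definition and tabulation and does not threaten the data.

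**What to change.** In 15.5 and the SAP, define the TEAE window for every patient, whether or not they leave the study, as the first AK002-016X infusion through 84 (±3) days after that patient's last infusion. This is the protocol's stated follow-up period. The SAP should state how the ±3-day allowance is applied, so that the cut can be programmed.

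Tabulate later events as post-treatment, with 85–120 days (the four-month, five-half-life interval) shown separately from anything later. Also keep the count of all events to end of study for serious events and for all AESIs, not malignancy alone.

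The cost is one sentence and one or two extra tables, from dates already collected. The downside is that some late off-drug events leave the headline percentage, but they remain tabulated and listed. If the SAP already sets an end date, 15.5 needs only to be brought into line and the post-treatment tables confirmed.

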---------------------------	--

Objective	The objective of the study is to generate open-label, longer-term safety, tolerability, and efficacy follow-up data in patients with EG and/or EoD who completed Study AK002-016 or Study AK002-012. This study also provides patients randomized to placebo in Study AK002-016 the option to receive active dosing.
Safety Endpoints	The safety and tolerability of AK002 will be assessed by determining the incidence, relationship to study drug, and severity of TEAE, withdrawals due to adverse events, vital signs, laboratory tests, changes in concomitant medication use due to adverse events, immunogenicity, and other safety parameters.
Pharmacodynamic/ Efficacy Endpoints	
 • Short-Form Health and Well Being Survey (SF-36) questionnaire • Gastrointestinal symptomatology (EG/EoD PRO questionnaire) • Change in blood eosinophil count • Change in eosinophil counts in gastric and/or duodenal biopsies
Study Population	
Patients who complete Study AK002-016 or Study AK002-012 will have the option to receive AK002 in an open-label manner.
 
A patient is categorized as having completed Study AK002-016 if 6 infusions of study drug are administered and the patient is followed at least through the Day 176 visit for AK002-016. Patients are followed under the AK002-016 study until they receive their first dose in the AK002-016X study.
 
A patient is categorized as having completed Study AK002-012 if the patient received all cohort-appropriate doses and was followed for 5 months after the last dose of study drug in AK002-012.

Patient Selection Criteria	
Inclusion Criteria
 
Patients are eligible for the study if all of the following criteria are met:
 
 1) Provide written informed consent. 2) Completed Study AK002-016, defined as having received 6 infusions of study drug and followed through at least Day 176 (± 3 days) or completed Study AK002-012, defined as having received the cohort-appropriate number of doses and followed for 5 months after last dose of study drug. 3) If patient is on preexisting dietary restrictions, willingness to maintain those restrictions until the seventh dose has been received. After the seventh dose, diet may be liberalized. 4) Able and willing to comply with all study procedures.

Patient Selection Criteria cont.	Inclusion Criteria cont.

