11.4.6 Anti-AK002 Antibodies

Serum samples for ADA determination will be processed and shipped frozen in accordance with the central laboratory manual and laboratory kit instructions. Blood will be collected for determination of ADA predose on Extension Days 1, 197, and 512 (± 3 days) or 35 (± 3) days after last dose of study drug if ET. If already collected within the last 28 days as part of the last study visit in AK002-016, a duplicate collection is not required on Extension Day 1. For patients entering from Study AK002-012, a baseline collection is required prior to the first dose of study drug in AK002-016X.

A central laboratory will analyze the sample for ADA using a validated assay method. Specific information on ADA sample collection, processing, storage, and shipment will be provided in the central laboratory manual. Blood samples for ADA will also be collected anytime an immunogenicity-related AE occurs.

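### Section 15.5 puts ADA under by-visit and reference-range laboratory summaries, and specifies neither a patient-level ADA incidence nor a rule for event-driven samples

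*Combined protocol and SAP*

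**What the plan says.** The Synopsis names immunogenicity among the safety endpoints ("changes in concomitant medication use due to adverse events, immunogenicity, and other safety parameters"), and Section 6.1 lists anti-drug antibodies again. Neither place defines a measure.

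The analysis is in Section 15.5, under Clinical Laboratory Assessments: "laboratory tests to be summarized include blood chemistry, hematology, urinalysis, and ADA". Two methods follow for that list:

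- "Descriptive statistics will be used to summarize laboratory results at baseline, each visit, and the change from baseline for each visit"
- "shift tables will summarize the laboratory results relative to normal reference ranges at baseline and each post-baseline time point"

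Three general statements at the opening of Section 15 also apply: "summary statistics of number and percentage will be computed for categorical variables"; "All patient data will be listed"; and "A separate Statistical Analysis Plan will describe data handling and statistical techniques in full detail".

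Section 11.4.6 schedules ADA samples predose on Extension Day 1, on Day 197, and on Day 512 (or 35 days after the last dose after early termination). It adds: "Blood samples for ADA will also be collected anytime an immunogenicity-related AE occurs".

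**The concern.** An ADA result is positive or negative, possibly with a titre. It has no normal reference range, so a shift table against one has no meaning, and a change from baseline does not define seroconversion. Immunogenicity is usually judged on how many patients become antibody-positive on treatment and whether those patients have more reactions or lower exposure. Section 15.5 asks for neither. The same section does specify patient incidence for treatment-emergent adverse events, so a patient-level count was thought of for events but not for ADA.

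This matters here because infusion-related reactions are the most common treatment-emergent event reported so far (Synopsis, Clinical Background; Section 2.3). Together with hypersensitivity and anaphylaxis they are adverse events of special interest (Section 13.3). The event-driven samples let antibodies be examined when such an event occurs, yet nothing says how those results enter a summary.

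**Working it through.** **No figure to reproduce.** The plan states no ADA rate, precision or power, and the 183 patients are an enrolment ceiling taken from the parent study (Sections 7.1 and 15.1). The check is a reading of the text plus one illustrative calculation.

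**What the text yields for ADA**

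| Quantity | Specified? |
|---|---|
| n (%) positive at each visit | Yes, by combining Section 15.5 with the categorical-data rule of Section 15 |
| Change from baseline | Yes, but undefined for a positive/negative result |
| Shift against a normal range | Yes, but ADA has no such range |
| Definition of positive, treatment-emergent or boosted | No |
| Patient-level count and its denominator | No |
| Rule for event-driven samples | No |
| Link to reactions, AK002 concentration or eosinophils | No (Sections 15.5 and 15.6) |

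**Sampling interval.** The Day 1 sample precedes Dose 1 and the Day 197 sample precedes Dose 8, so 7 infusions over 197 − 1 = 196 days separate them. From Day 197 to Day 512 is 315 days with 11 infusions (Doses 8 to 18). Between these points, event-driven samples are the only ADA information. If such a sample were placed in, say, a Day 29 column, that column would hold only patients with a suspected event, and its percentage would have no usable denominator.

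**By-visit positivity against ever-positive.** Let p1 and p2 be the prevalences at the two scheduled post-baseline samples, among patients who have both. Then

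ever-positive = p1 + p2 − overlap.

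Take p1 = p2 = p, and let f be the share of Day 197 positives still positive at Day 512. Then ever-positive = 2p − fp, which runs from p (f = 1) to 2p (f = 0). All p and f are assumed; patient counts use 183.

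| p at each visit | Patients per visit | f = 1 | f = 0.5 | f = 0 |
|---|---|---|---|---|
| 2% | 3.7 | 2% (3.7) | 3% (5.5) | 4% (7.3) |
| 5% | 9.2 | 5% (9.2) | 7.5% (13.7) | 10% (18.3) |
| 10% | 18.3 | 10% (18.3) | 15% (27.5) | 20% (36.6) |

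With unequal prevalences the same limit holds against the larger column, because (p1 + p2) / max(p1, p2) is at most 2.

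**Baseline.** A by-visit column also counts patients who were already positive on Day 1, so it does not measure treatment-emergent ADA either. Former placebo patients from AK002-016 enter alongside patients already given AK002 (Synopsis, Study Design and Objective). Extension Day 1 is therefore drug-naive for some and not for others, and a change from it mixes two different quantities.

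**Event-driven sampling.** The documents disagree on whether it is required. Section 11.4.6 and Table 1 note 19 make it mandatory. Section 6.2 and the infusion-visit lists in Section 12 (12.2 to 12.9 and 12.11) make it optional.

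**The case against.** Three stronger readings are tempting, and the documents support none of them.

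- **That ADA will be summarised with means.** Section 15.5 says descriptive statistics, and Section 15 gives number and percentage for categorical variables. A positive/negative result would get n (%) by visit.
- **That the trial will yield no ADA incidence.** All patient data are listed, so an ever-positive count could be derived afterwards. A separate Statistical Analysis Plan is promised, and none of its text is in the supplied document. It may already define the analysis. What can be said is that Section 15.5 specifies no incidence.
- **That event-driven samples are excluded.** The laboratory paragraph refers to each visit and does not limit this to scheduled visits; that limit appears only in Section 15.6, for blood eosinophils. Their absence from the summaries is an inference from the missing rule, and they would still be listed.

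It is also fair to say that the size rests on assumptions. If ADA persists, the same patients are positive at both visits and the by-visit figure equals ever-positive. Nor does pooling the scheduled samples recover antibodies that appear and disappear between them. Finally, this is a descriptive open-label extension with no formal inference, so no test or claim depends on the point.

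What stands is the specification gap. A listing is not a prespecified analysis with a definition and a denominator, and the reference-range shift and change-from-baseline summaries are assigned to ADA in the plan's own text.

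**Conclusion.** The point holds as a gap in specification and a mismatch of method. Section 15.5 assigns ADA a generic laboratory method that gives, at best, n (%) positive by visit. It leaves a named safety endpoint without a patient-level measure, status categories or a rule for event-driven samples. By-visit positivity at Days 197 and 512 can understate ever-positive by a factor of between one and two, before counting patients positive only on an event-driven sample. That range assumes equal prevalence at the two samples and patients with both; where in it the trial would fall depends on how long antibodies persist, which the documents do not say. The change should be made, but it corrects a descriptive analysis and does not call the study's conduct into question.

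**What to change.** 1. In Section 15.5, take ADA out of the change-from-baseline and reference-range shift summaries.
2. Report n (%) of patients with treatment-emergent ADA (baseline negative, then any post-baseline positive) and n (%) ever-positive post-baseline. Use all post-baseline samples, unscheduled ones included, with patients having at least one post-baseline sample as the denominator. Add a boosted category only if the assay reports titre; Section 11.4.6 says only that the assay is validated.
3. State which baseline is used, and present results by prior AK002 exposure (former placebo versus previously treated).
4. Cross-tabulate ADA status with infusion-related and hypersensitivity events of special interest. List it beside AK002 concentration, where sampled, and predose eosinophil count.
5. Reconcile the mandatory wording for event-driven ADA samples (Section 11.4.6, Table 1 note 19) with the optional wording (Sections 6.2 and 12).
6. If the separate Statistical Analysis Plan already covers this, align Section 15.5 with it.

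The cost is one paragraph and two tables. No new samples or visits are needed.
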